18.0 DATA AND SAFETY MONITORING PLAN

18.1 Trial monitoring

Institutional support of trial monitoring will be in accordance with the FHCRC/University of Washington Cancer Consortium Institutional Data and Safety Monitoring Plan. Under the provisions of this plan, FHCRC Clinical Research Support (CRS) coordinates data and compliance monitoring conducted by consultants, contract research organizations, or FHCRC employees unaffiliated with the conduct of the study. Independent monitoring visits occur at specified intervals determined by the assessed risk level of the study and the findings of previous visits per the institutional DSMP. It will be the monitor's responsibility to inspect the CRFs at regular intervals throughout the study to verify both adherence to the protocol and the completeness, consistency, and accuracy of the data being entered on them.

In addition, protocols are reviewed at least annually and as needed by the Consortium Data and Safety Monitoring Committee (DSMC), FHCRC Scientific Review Committee (SRC), and the FHCRC/University of Washington Cancer Consortium Institutional Review Board (IRB). The review committees evaluate accrual, adverse events, stopping rules, and adherence to the applicable data and safety monitoring plan for studies actively enrolling or treating subjects. The IRB reviews the study progress and safety information to assess continued acceptability of the risk-benefit ratio for human subjects. Approval of committees as applicable is necessary to continue the study.

The trial will comply with the standard guidelines set forth by these regulatory committees and other institutional, state and federal guidelines.

18.2 Data and safety review

Investigators will conduct continuous review of data and patient safety. At least monthly review meetings are required and will include: PI, data manager, study coordinator, and other members as per the PI's discretion (e.g. sub-investigators, nurses).

Review of data and patient safety will be reviewed during these meetings, including:

- The number of patients enrolled in the protocol
- Any significant toxicities experienced by patients enrolled
- Dose modifications and responses observed

19.0 STUDY DOCUMENTATION AND RECORD-KEEPING

19.1 Investigator's files and retention of documents

The investigator must maintain adequate and accurate records to enable the conduct of the study to be fully documented and the study data to be subsequently verified. These documents should be classified into two separate categories as follows: (1) the investigator's study file, and (2) subjects' clinical source documents.

The investigator's study file will contain the protocol and protocol amendments, CRFs, query forms, IRB/EC and governmental approvals with correspondence, sample informed consent, drug records, staff curriculum vitae and authorization forms, any other records required under the Protocol, and other appropriate documents and correspondence.

Subjects' clinical source documents include the subjects' hospital/clinic records; physicians' and nurses' notes; original laboratory, ECG, X-ray, pathology and special assessment reports; signed informed consent forms; consultant letters; and subject screening and enrollment logs.

The investigator must keep these two categories of documents on file for at least the latest of (a) 2 years following the marketing application approval date for the study treatment in the indication being investigated, or (b) 2 years after the investigation is completed or discontinued, or (c) for a period of time consistent with local regulatory requirements, whichever is longest. After that period, the documents may be destroyed subject to local regulations with prior written permission from Exelixis/Merck. If the investigator wants to assign the study records to another party or move them to another location, Exelixis/Merck must be notified in advance.

19.2 Source documents and background data

Upon request, the investigator will supply its licensees and collaborators with any required background data from the study documentation or clinic records. This is particularly important when CRFs are illegible or when errors in data transcription are suspected. In case of special problems or governmental queries or requests for audit inspections, it is also necessary to have access to the complete study records, provided that subject confidentiality is protected.

19.3 Audits and inspections

The investigator should understand that source documents for this study must be made available, after appropriate notification, to qualified personnel from the Exelixis or Merck Quality Assurance Unit (or designee) or to health authority inspectors. The verification of the CRF data must be by direct inspection of source documents.

19.4 Case report forms

For enrolled subjects, only data from the procedures and assessments required by the CRFs should be entered on the appropriate CRF. Other are recorded only on the source documents and will not be transcribed to CRFs. Additional procedures and assessments may be performed as part of the

investigator's institution or medical practice standard of care and may not be required for CRF entry.

For each subject enrolled, the CRF (paper or electronic) must be completed and signed by the PI or authorized delegate from the study staff.

All paper forms should be typed or filled out using indelible ink and must be legible. Errors should be crossed out but not obliterated, the correction inserted, and the change initialed and dated by the investigator or his or her authorized delegate.

The investigator should ensure the accuracy, completeness, legibility, and timeliness of the data in the CRFs and in all required reports.

20.0 PROTOCOL MODIFICATIONS

Protocol modifications or amendments must be reviewed and approved by Exelixis and Merck prior to implementation. All protocol modifications must be submitted to the IRB/EC for information and approval in accordance with local requirements and to regulatory agencies if required. Approval must be obtained before any changes can be implemented, except for changes necessary to eliminate an immediate hazard to study subjects or those that involve only logistical or administrative aspects of the trial (e.g. change in monitor or change of telephone number).

21.0 TERMINATION OF STUDY

At any time, the study may be terminated prior to completion of planned enrollment and achievement of objectives if there is evidence that the study regimen is not tolerable at the lower dose limits stated in the protocol, or if interim data analysis demonstrates lack of efficacy of study treatment. In terminating the study, the investigator will ensure that adequate consideration is given to the protection of the subjects' interests.

Upon study termination, the investigator shall cease enrolling subjects into the study and shall discontinue conduct of the study as soon as is medically practicable. The IRB will be notified about the completion or early termination of the trial.

22.0 ETHICAL ASPECTS

22.1 Local regulations

The study must fully adhere to the principles outlined in ICH Good Clinical Practice (GCP) and local regulations on the conduct of clinical research.).

22.2 Institutional review board/ethics committee

This protocol (and any modifications) and appropriate consent procedures must be reviewed and approved by an IRB/EC. This board must operate in accordance with current local, regional, and federal regulations. The investigator will send a letter or certificate of IRB/EC approval to Exelixis and Merck (or designee) before subject enrollment and whenever subsequent modifications to the protocol are made.

22.3 Confidentiality of trial documents and subject regions

The investigator must assure that subjects' anonymity will be maintained and that their identities are protected from unauthorized parties. On CRFs or other documents, subjects should be identified by identification codes and not by their names. The investigator should keep a subject enrollment log showing codes, names, and addresses. The investigator should maintain documents (e.g. subjects' written consent forms) in strict confidence.

All tumor scans, research samples, photographs, and results from examinations, tests, and procedures may be sent to Exelixis and Merck, and its partners or designees for review.

23.0 PUBLICATION OF DATA

The PI holds the primary responsibility for publication of the study results, provided that the PI will provide Exelixis and Merck with a copy of any proposed publication or release:

- (a) for abstracts, slide presentations or posters, at least five (5) business day prior to submission (in the case of abstracts) or first public presentation (in the case of slide presentations and posters); and
- (b) at least thirty (30) days in advance of first submission and each subsequent submission in the case of manuscripts and also comply with any provisions regarding publication that are agreed to between the University of Washington and Exelixis and Merck in the Clinical Trial Agreement related to this study.

24.0 APPENDICES

Appendix 1: Abbreviations and definitions

Abbreviation or term	Definition
AE	Adverse event: any untoward medical occurrence in a patient or clinical investigation patient administered a pharmaceutical product and that does not necessarily have a causal relationship with this treatment. An adverse event can therefore be any unfavorable and unintended sign (including an abnormal laboratory finding), symptom, or disease temporally associated with the use of a medicinal (investigational) product, whether or not related to the medicinal (investigational) product.

ALP	alkaline phosphatase
ALT	alanine aminotransferase
ANC	absolute neutrophil count
AUC	area under the curve
AST	aspartate aminotransferase
BP	blood pressure
CBC	complete blood count
CI	confidence interval
CMV	Cytomegalovirus
CR	complete response
CRF/eCRF	case report form/electronic case report form
CT	computed tomography
CTCAE	Common Terminology Criteria for Adverse Events
CYP	cytochrome P450
DCR	disease control rate
DILI	drug-induced liver injury
DNA	deoxyribonucleic acid
DSMC	data and safety monitoring committee
DVT	deep venous thrombosis
EBV	Epstein-Barr virus
eDC:	Electronic Data Capture. A computer database where clinical trial data are entered and validated.
ECOG	Eastern Cooperative Oncology Group
EKG	electrocardiogram
Enrollment:	The act of assigning a patient to a treatment. Patients who are enrolled in the trial are those who have been assigned to a treatment.
Enter:	Patients entered into a trial are those who sign the informed consent form directly.
ERB/IRB	ethical review board / institutional review board
FFPE	formalin-fixed, paraffin-embedded
GCP	good clinical practice
GFR	glomerular filtration rate
GLP	good laboratory practice
GI	gastrointestinal
Hb	hemoglobin
HBeAb	hepatitis B e-antigen antibody
HBeAg	hepatitis B e-antigen antigen
HBcAb	hepatitis B core antibody
HBsAb	hepatitis B surface antibody
HBsAg	hepatitis B surface antigen
HBV	hepatitis B virus
HCV	hepatitis C virus
HR	hazard ratio
i (prefix)	immune
IB	investigator's brochure
ICF	informed consent form

iCPD	immune confirmed progressive disease
IHC	immunohistochemistry
INR	international normalized ratio
Investigational product (IP):	A pharmaceutical form of an active ingredient or placebo being tested or used as a reference in a clinical trial, including products already on the market when used or assembled (formulated or packaged) in a way different from the authorized form, or marketed products used for an unauthorized indication, or marketed products used to gain further information about the authorized form.
irAE	immune-related adverse event
IRB	institutional review board
iUPD	immune unconfirmed progressive disease
IV	intravenous
LMWH	low molecular weight heparin
NSAIDS	non-steroidal anti-inflammatory drugs
MI	myocardial infarction
MRI	magnetic resonance imaging
OS	overall survival
ORR	objective response rate
PI	principal investigator
PD	progressive disease
PD-1	programmed cell death 1
PE	physical exam
PET	positron emission tomography
PFS	progression-free survival
PK	pharmacokinetic
PO	orally
PPES	palmar-plantar erythrodyesthesia syndrome
PR	partial response
PTT	partial prothrombin time
QTc	corrected QTc interval (QTcF: QTc calculated by Fredericia formula)
RECIST	Response Evaluation Criteria In Solid Tumors
iRECIST	immune RECIST
mRECIST	modified RECIST
RBC	red blood cell
Reporting database:	A point-in-time copy of the collection database. The final reporting database is used to produce the analyses and output reports for interim or final analyses of data.
Re-screen:	To screen a patient who was previously declared a screen failure for the same study.
RPLS	reversible posterior leukoencephalopathy syndrome
SAE	serious adverse event
Screen:	The act of determining if an individual meets minimum requirements to become part of a pool of potential candidates for participation in a clinical study.
Screen failure:	Patient who does not meet one or more criteria required for participation in a trial.
SD	stable disease

TEAE	treatment-emergent adverse event
TIA	transient ischemic attack
TRAЕ	treatment-related adverse event
TSH	thyroid-stimulating hormone
UPCR	urine protein to creatinine ratio
ULN	upper limit of normal
WBC	white blood cell
WOCP	women of child-bearing potential

Appendix 2. Cabozantinib Drug Diary

Today's Date: _____

Participant Study ID: _____

Participant Initials: _____

Cycle Number: _____

INSTRUCTIONS TO THE PARTICIPANT:

1. Complete one form for each cycle (21 days).
2. You will take 40 mg of Cabozantinib (2) x (20 mg pills) once a day. Or 20 mg of Cabozantinib if dose reduced (1) x (20 mg pill).
 - Cabozantinib must be taken daily on an empty stomach. You must not eat for at least 2 hours before and at least 1 hour after taking Cabozantinib.
 - Take your Cabozantinib dose at approximately the same time every day.
 - Cabozantinib pills should be swallowed whole with at least 8 ounces of water.
3. Record the date, the number of pills you took, and the time that you took them.
4. If you have any comments or notice any side effects, please record them in the comments column.
5. Please bring your pill bottle and this form to your physician when you go to your next appointment.
6. Please record missed or skipped doses. Do not share your drug supply. Wash your hands after touching the pills.
 - The dose may be taken later only if it is within 12 hours of when the missed dose should have been taken.
 - The missed dose should not be made up if it is within 12 hours of the next scheduled dose.
7. The tablets should not be crushed. Grapefruit, grapefruit juice, Seville oranges, star fruit, and their products should be avoided.

Date	Day	DOSE		Comments
		Number of Pills Taken	Time dose was taken	
	1			
	2			
	3			
	4			
	5			
	6			
	7			
	8			
	9			

RG100703410			
-------------	--	--	--

	11			
	12			
	13			
	14			
	15			
	16			
	17			
	18			
	19			
	20			
	21			
	22			
	23			
	24			
	25			
	Participant's Signature: _____ Date: _____			
	Physician's office will complete this section: Number of tablets dispensed: _____ Date of pills dispensed: _____ Participant's planned daily dose: _____ Total number of pills taken this month: _____ Has the patient missed any study medication?  Yes  No Comments: _____ Study Personnel Signature: _____ Date: _____			

Medical EMERGENCY: 911 (such as chest pain, seizure, sudden shortness of breath, etc.)

Research Coordinator: _____ / Weekday Pager Number: _____
 24-hour EMERGENCY [contact]

Appendix 3: Clinical laboratory tests

Hematology (at screening and on study)	Serum chemistry (at screening and on study)
Hemoglobin Hematocrit Leukocytes (WBC) Neutrophils (segmented and bands) Lymphocytes Monocytes Eosinophils Basophils Platelets	Sodium Bicarbonate (CO ₂) Potassium Calcium Magnesium Phosphate Glucose Albumin Total protein Blood urea nitrogen (BUN)
	Creatinine Alanine aminotransferase (ALT) Aspartate aminotransferase (AST) Alkaline phosphatase (ALP) Total bilirubin
Coagulation (at screening and on study) International normalized ratio (INR) Partial thromboplastin time (PTT)	HBV/HCV status At screening: 
- HCV Ab (if positive, obtain HCV RNA)- HBcAb, HbsAg (if either or both are positive, obtain HBV DNA) On study: 
- HBcAb+ and HBsAg- at baseline: obtain HBsAg every 2 cycles starting at cycle 3 (and HBV DNA if positive)- HBcAb+ and HBsAg+ at baseline: obtain HBV DNA every 2 cycles starting at cycle 3
Other immune-related AE monitoring (at screening and every 2 cycles on study starting at cycle 3) TSH, free T4 and T3 Cortisol Amylase Lipase	Urine protein (at screening and every 2 cycles starting at cycle 3) Urine protein to creatinine ratio
Tumor marker (at screening and every 3 cycles starting at cycle 4) Alpha fetoprotein	Serum pregnancy test (women of childbearing potential only) at screening only

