 - h. Serum creatinine $\leq 1.5 \times \text{ULN}$ or calculated creatinine clearance $\geq 40 \text{ mL/min}$ using the Cockcroft-Gault equation (Appendix 7).
 - i. Urine protein/creatinine ratio (UPCR) $\leq 1 \text{ mg/mg}$ ($\leq 113.2 \text{ mg/mmol}$) or 24h urine protein $\leq 1\text{g}$.
 - j. Hemoglobin A1c (HbA1c) $\leq 8\%$ within 28 days before randomization or fasting serum glucose $\leq 160 \text{ mg/dL}$.
11. Patients with positive hepatitis B surface antigen (HBsAg) and/or HBV viral load $>100 \text{ IU/mL}$ at the time of enrollment are eligible to enroll on study if they meet the following criteria:
 - a. Anti-HBV therapy as per institutional practice must be given at least 4 weeks and HBV viral load must be $<100 \text{ IU/mL}$ prior to initiating study treatment. Patients on active HBV therapy with viral loads $<100 \text{ IU/mL}$ should remain on the same therapy throughout study treatment.
 - b. Note: Patients with positive anti-hepatitis B core antibody (HBcAb), negative HBsAg, and negative or positive anti-hepatitis B surface antibody, and who have an HBV viral load $<100 \text{ IU/mL}$ do not require anti-viral prophylaxis.
12. Patients with past or ongoing hepatitis C infection (HCV) are eligible to enroll on study, with or without prior anti-viral treatment, as long as the other eligibility criteria are met. Treated patients must have completed their anti-viral treatment at least 1 month prior to initiating study treatment.
13. Sexually active fertile subjects and their partners must agree to use effective methods of contraception (see Appendix 8) during the course of the study and for at least 4 months after the last dose cabozantinib. They must also refrain from donating sperm during this time period.
14. Female subjects of childbearing potential must not be pregnant at screening and not breastfeeding. Females of childbearing potential are defined as premenopausal females capable of becoming pregnant (i.e. females who have had any evidence of menses in the past 12 months, with the exception of those who had prior hysterectomy).
 - a. Women who have been amenorrheic for 12 or more months are still considered to be of childbearing potential if the amenorrhea is possibly due to prior chemotherapy, antiestrogens, low body weight, ovarian suppression or other reasons.
15. Capable of understanding and complying with the protocol requirements and must provide written informed consent/assent for the study.

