18. Patients with proteinuria >1+ on urine dipstick testing will undergo 24-hour urine collection for quantitative assessment of proteinuria. Participants with urine protein ≥ 1 g/24 hours will be ineligible.
19. Corrected QT interval calculated by the Fridericia formula (QTcF) > 480 ms per electrocardiogram (EKG) within 28 days before first dose of study treatment.
 - a. Note: If a single EKG shows a QTcF with an absolute value > 500 ms, two additional EKGs at intervals of approximately 3 min must be performed within 30 min after the initial EKG, and the average of these three consecutive results for QTcF will be used to determine eligibility.
20. Inability to swallow tablets or any other condition that might interfere with oral absorption of medications.
21. Previously identified allergy or hypersensitivity to study drugs and/or any of their excipients.
22. Ongoing secondary malignancy that is progressing and/or has required active treatment within the past year. Adjuvant treatment for resected breast cancer is allowed.
 - a. Subjects with basal cell carcinoma of the skin, squamous cell carcinoma or the skin, prostate cancer, or carcinoma in situ (e.g. breast carcinoma, cervical cancer in situ) that have undergone potentially curative therapy are allowed.
23. Has a known history of HIV infection. Note: HIV testing is not mandated for screening.
24. Co-infection with HBV (HBsAg (+) and /or detectable HBV DNA) and HCV (anti-HCV Ab (+) and detectable HCV RNA) at study entry.
25. Co-infection with HBV and HDV at study entry.
26. Live vaccine or live attenuated vaccine within 30 days prior to first dose of study treatment.
Administration of killed vaccines is allowed.
27. Pregnant or lactating females.
28. Known psychiatric illness, substance abuse disorder, or other condition that would interfere with the ability to comply with the requirements of the study.
29. Has history or current evidence of any condition, therapy, or laboratory abnormality that might confound the results of the study, interfere with the subject's participation for the full duration of the study, or is not in the best interest of the subject to participate, in the opinion of the treating investigator.

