6.2 Screening

Written informed consent must be obtained before initiation of any clinical screening procedure that is performed solely for the purpose of determining eligibility for this study. Evaluations performed as part of routine care before informed consent can be considered as screening evaluations if done within the defined screening period.

Study eligibility is based on meeting all of the study inclusion criteria and none of the exclusion criteria at screening and on Study Day 1 before study treatment administration.

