6.3 Subject registration

Once screening procedures are completed and eligibility is confirmed, the study subject will be registered and entered into the Clinical Trial Management System (CTMS) at the Fred Hutchinson Cancer Center. All patients must be registered and be assigned a unique study number prior to starting protocol therapy. Treatment initiation must occur within 5 working days of registration.

If a patient is consented to the trial but is not registered or is withdrawn prior to initiation of protocol treatment, the reason for screen failure and/or withdrawal will be documented. However, no clinical trial data will be collected beyond the basic demographic data contained on the eligibility checklist. A registration log with dated entries for each patient registered will be kept.

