10.0 STUDY CALENDAR

Table 10.1 summarizes the trial procedures to be conducted at various timepoints. It may be necessary to perform these procedures at unscheduled time points if deemed clinically necessary by the investigator. Furthermore, additional evaluations/testing not outlined in this table may be deemed necessary by the Principal Investigator for reasons related to participant safety.

Table 10.1. Baseline schedule of activities

1 cycle = 21 days	Baseline ¹⁷	Cycle 1			Cycle 2+ Day 1 (± 2 days)	Treatment discontinuation visit ¹⁹ (+ 7 days)	Follow-up ²⁰ (± 7 days)
		Day 1 ¹⁸	Day 8 (± 2 days)	Day 15 (± 2 days)			
TREATMENT							
Cabozantinib ¹		X	X	X	X		
Pembrolizumab ²		X			X		
REQUIRED ASSESSMENTS							
Informed consent/HIPAA	X						
Inclusion/exclusion criteria ³	X						
Medical and smoking history	X						
Disease and treatment history	X						
Vital signs, physical exam, ECOG status, weight ⁴	X	X	X	X	X	X	
Height ⁵	X						
AE and medications assessment ⁶	X	X	X	X	X	X	
Cabozantinib Drug Diary Collection ⁷		X			X	X	
CBC and differential ⁸	X	X		X	X	X	
Serum chemistry ⁸	X	X		X	X	X	
PT/INR, PTT	X	X			X	X	
Lactate dehydrogenase	X						
Hepatitis C antibody (+/- HCV RNA) ⁹	X						
Hepatitis B core antibody ¹⁰	X						
Hepatitis B surface antigen and/or HBV	X				X (q2C starting)		

DNA ¹⁰					at C3)		
TSH with reflex T4 ¹¹	X				X (q2C starting at C3)		
Cortisol ¹¹	X				X (q2C starting at C3)		
Amylase ¹¹	X				X (q2C starting at C3)		
Lipase ¹¹	X				X (q2C starting at C3)		
Urinary protein to creatinine ratio ¹¹	X				X (q2C starting at C3)		
EKG ¹¹	X				X (q2C starting at C3)		
Esophagoduodenoscopy (EGD) ¹²	X						
Pregnancy test (WOCOP only)	X						
Vital status, date of progression if applicable						X	X
DISEASE ASSESSMENT							
Alpha fetoprotein ¹³	X				X (q3C starting at C4)	X	
Radiologic imaging by CT or MRI ¹⁴	X				X (q3C starting at C4)	X	X
CORRELATIVE STUDIES							
Archival tumor tissue for research purposes if available. Otherwise, fresh biopsy is optional. ¹⁵	X						
Blood collection ¹⁶		X	X		X (C2D1 only)		

Footnotes

¹Daily continuously starting at Cycle 1 Day 1. See Section 9.0 for dose modifications.

²Dosed on Day 1 of each 3-week cycle. See Section 9.0 for dose modifications.

³See Section 5.0 for inclusion and exclusion criteria.

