¹²EGD must be done within 6 months prior to study initiation to assess for and treat esophageal and gastric varices.

¹³Alpha fetoprotein (AFP) should be measured at baseline (within 14 days prior to registration). If abnormal at baseline, it should be measured on Day 1 of every 3 cycles starting at cycle 4, and at the treatment discontinuation visit.

¹⁴Disease assessment using multiphasic (four-phase) contrast CT or MRI of abdomen/pelvis, as well as CT chest with or without contrast should be done at baseline (within 28 days prior to registration), and every 9 weeks on treatment (every 3 cycles). If there is disease progression and the patient continues on treatment beyond progression, repeat imaging must be performed 4 weeks later to confirm progression. As clinically indicated, bone scan and contrast imaging of neck may be obtained to monitor disease (see Section 13.3). For the treatment discontinuation visit, the most recent scans are used. For patients who come off study for toxicity, subsequent restaging scans will be requested and assessed at least every 4 months for up to 2 years from study start date to document the date of progression.

¹⁵Archival tumor tissue is acceptable (paraffin-embedded tumor core biopsy or surgical specimen). If archival tissue is not available, baseline core needle biopsy may be performed (if safe and feasible).

¹⁶Pre-treatment Blood will be collected and stored for correlative studies. Research blood will be collected on Cycle 1 Day 1 and Day 8, as well as Cycle 2 Day 1.

¹⁷Informed consent/HIPAA, medical/smoking history, AE/medication assessment, physical exam/ECOG, and assessment of inclusion/exclusion criteria are completed within 28 days prior to registration. Baseline lab investigations are completed within 14 days prior to registration, including pregnancy test for women of child-bearing potential (WOCP) and AFP. Baseline imaging for disease assessment may be obtained within 28 days prior to registration.

¹⁸Cycle 1 day 1 testing need not be repeated if completed within 7 days prior.

¹⁹The treatment discontinuation visit should occur 30 days (+7 days) after the last dose of cabozantinib or pembrolizumab (whichever is latest). Most recent scans are used for the treatment discontinuation visit. Note: if a participant initiates a new anti-cancer therapy within 30 days after the last dose of trial

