- Pregnancy test by serum HCG (for women of child-bearing potential only).
- Alpha fetoprotein.

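### The single pregnancy test is tied to first dose only through registration, so it may be up to about 21 days old at dosing, and no test is scheduled to support the Study Day 1 eligibility condition

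*Combined protocol and SAP*

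**What the plan says.** The test appears in three places, and all three agree. Table 10.1 marks it in the Baseline column only. Section 11.1 lists it among the screening laboratory tests. Appendix 3 restricts it: "Serum pregnancy test (women of childbearing potential only) at screening only". Section 11.2 lists no pregnancy test on study.

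Its window is counted back from registration. Footnote 17 to Table 10.1 states: "Baseline lab investigations are completed within 14 days prior to registration, including pregnancy test". Section 6.3 then sets the next interval: "Treatment initiation must occur within 5 working days of registration".

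Two eligibility criteria concern pregnancy. Inclusion 14 fixes the time point at screening: "Female subjects of childbearing potential must not be pregnant at screening and not breastfeeding". Exclusion 27 has no time point of its own: "Pregnant or lactating females". Section 6.2 supplies one, because a patient must meet "none of the exclusion criteria at screening and on Study Day 1 before study treatment administration".

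**The concern.** Section 6.2 makes absence of pregnancy a condition on the day of first dose, yet the only scheduled evidence comes from screening. Other safety checks are tied more closely to dosing. Inclusion 6 requires Child-Pugh class A within 7 days before first dose. Inclusion 10 requires the organ and marrow tests within 14 days before first dose. Blood count, chemistry and coagulation are repeated on Cycle 1 Day 1 unless done in the preceding 7 days (footnote 18). The pregnancy test falls under none of these rules: it is not among the inclusion 10 items, and it has no Day 1 entry for footnote 18 to act on.

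What is at stake is patient safety. A woman who conceived around or after the screening test could receive the first dose of both drugs although every scheduled test had been done. The remaining safeguards do not require detection before that dose. Contraception under inclusion 13 lowers the risk but detects nothing. Pregnancy monitoring under Section 16.4.2 begins at treatment initiation. Section 12.0 stops treatment in a woman who becomes pregnant, which is after exposure.

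**Working it through.** The plan states no figure for the age of the test at first dose, so there is none to reproduce. The maximum follows from calendar arithmetic.

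**Inputs**
- Test to registration: at most 14 days (footnote 17; Section 11.1).
- Registration to first dose: at most 5 working days (Section 6.3).
- Assumptions: registration on a weekday, a Monday-to-Friday working week, and the registration day not counted.

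**Maximum test age at first dose = days from test to registration + calendar days from registration to first dose**

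Five working days always span one weekend, so they equal 7 calendar days from any weekday.

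| Reading of Section 6.3 | Calendar days | Maximum test age |
|---|---|---|
| No public holiday, registration day not counted | 7 | 14 + 7 = 21 |
| Registration day counted as working day 1 | 4 (Monday) or 6 (Tuesday to Friday) | 18 or 20 |
| One public holiday in the interval | 8 (Monday to Thursday) or 10 (Friday) | 22 or 24 |

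**Age under other arrangements**
- Sample drawn with the panel that satisfies inclusion 10: at most 14 days before first dose. To exceed 14 days, a site must draw the pregnancy test early and use a later panel for inclusion 10. The plan permits this.
- Cycle 1 Day 1 entry with the footnote 18 allowance: at most 7 days, a reduction of 21 − 7 = 14 days.
- Test done on Day 1: 0 days.

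**Patients concerned**

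Section 1.1 puts the risk of HCC in men at 3.5 times that in women. If enrolment followed that ratio (an assumption), the expected number of women would be 29 / (3.5 + 1) = 6.4, or about 6. Women of childbearing potential are a subset of these, and the documents give no age distribution. The plausible range is therefore 0 to about 6; the upper figure is an expectation and not a hard cap.

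**The case against.** The strongest reply is that this is a deliberate and consistent choice. Every place that schedules the test says the same thing, and inclusion 14 sets the same time point. The window is not unusual within this protocol: the footnote 11 tests and AFP share it, and QTcF is accepted up to 28 days before first dose. On Day 1 the investigator has a duty under Section 6.2, examines the patient, and may order an unscheduled test under Section 10.0. Contraception is an entry condition.

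Most of this stands as fact, and it limits the point. It does not remove it, because nothing in that list makes a test before dosing mandatory.

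Three stronger readings are tempting, and the documents do not support them:
- A reader might infer that nothing limits the age of the test at first dose. A limit exists; it runs indirectly, through registration.
- A reader might infer that the plan contradicts itself. Section 6.2 sets a condition but orders no repeat test, and inclusion 14 speaks only of screening.
- A reader might take 21 days as the usual age. It is a ceiling. Sites that draw the sample with the inclusion 10 panel will be at 14 days or less.

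It is also fair to object that a 7-day allowance is not Day 1 evidence either. That is correct: the allowance narrows the gap, and only a test on Day 1 brings the age to zero. The case for 7 days is that the protocol already uses it for the other Day 1 laboratory tests.

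**Conclusion.** The point holds as a gap in safety scheduling. A compliant site may dose on a pregnancy result up to about 21 calendar days old (18 to 24 across the readings of the working-day rule), and no scheduled test supports the Study Day 1 condition.

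The practical size is small. The documents give no probability of conception in the interval, so the number of exposures prevented cannot be estimated and may be zero. Response rate, error rates and sample size are untouched. The change is worth making because it is cheap and the harm, though rare, could be irreversible. It does not need an amendment of its own.

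**What to change.** In Table 10.1 (Cycle 1 Day 1 column), Section 11.2 and Appendix 3, add for women of childbearing potential: a pregnancy test on Cycle 1 Day 1, with a negative result required before the first dose; it need not be repeated if done within the 7 days before (the footnote 18 rule). The words in Appendix 3 that confine the test to screening must change to match.

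Use the clinical safety-laboratory draw for Cycle 1 Day 1 where possible. If those tests are waived under footnote 18 and no pregnancy test was done within 7 days, take a separate clinical sample. The Day 1 research blood should not be used, because Section 15.1 confines those data to the correlative studies.

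The cost is one line in each of three places and at most one extra assay per woman of childbearing potential, or none if her screening test already falls within 7 days. Under the sex-ratio assumption that is 0 to about 6 assays for the whole trial. The downsides are that the result must be back before dosing and that a separate sample will sometimes be needed. Section 20.0 requires review by both supporting companies and the IRB, so the change is best bundled with the next amendment.
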